8.3 SAMPLE SIZE DETERMINATION

The total sample size of 234 (117 per arm) was determined based on the number of adolescents with T1D who are annually transferred to adult diabetes care at each participating site:

- Ontario (4 sites total): The Hospital for Sick Children, Children's Hospital of Eastern Ontario (CHEO), Markham Stouffville Oaklands and Trillium Health Partners. The total number of patients annually transferred from these Ontario pediatric diabetes centers to adult diabetes centers is approximately 202. Thus, over an 21-month period, there will be approximately 303 patients transferred to adult diabetes care who are eligible to participate in this trial. We estimate, based on prior experience of the investigators involved in transition research, that we would be able to make contact, recruit, consent and enroll approximately half (152) of the eligible patients (303), and account for 20% (30) being lost to follow-up, we will have approximately 120 participants from Ontario sites enrolled in this trial.
- Quebec (2 sites total): Montreal Children's Hospital and CHU Saint Justine. The total number of patients annually transferred from both pediatric diabetes centers to adult diabetes centers is approximately 152. Thus, over an 21-month period, there will be approximately 228 patients transferred to adult diabetes care who are eligible to participate in this trial. We estimate, based on prior experience of the investigators involved in transition research, that we would be able to make contact, recruit and enroll approximately half (114) of the eligible patients (228), and account for 20% (23) being lost to follow-up, we will have approximately 90 participants from Quebec sites enrolled in this trial.

We have a conservative sample size of 234 (117 per arm) that will provide more than 80% power of detecting a between-group change in mean score for self-efficacy with diabetes management (SEDM) of 0.75, this accounts for 20% loss to follow-up at the 5% significance level (alpha) using a two-sample equal-variance t-test.

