8.4 POPULATIONS FOR ANALYSES

The conventional frequentist analyses are often interpreted in a dichotomous matter, based on the p-value chosen as threshold for 'statistical significance' and 'no evidence of effect' is confounded with 'evidence of no effect'. A Bayesian analysis will be conducted to provide the probability of any benefit or harm. An intention-to-treat analysis will be conducted by blinded analysts. We will evaluate the extent of missing data to determine if values are missing at random or not and will consider imputation to account for missing values.

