8.5.2 ANALYSIS OF THE PRIMARY ENDPOINT(S)

We will compare the mean SEDM score at 12 months between those in the intervention (regardless of original or modified) versus control arms. This will be done using linear regression to estimate the effect of the KiT intervention on self-efficacy of diabetes management, controlling for baseline SEDM. The linear model will be estimated using Bayesian linear mixed effect model accounting for the clustering of patients at their pediatric diabetes clinic using integrated nested Laplace approximation (INLA). We will adjust our analysis by sex and gender. The results will be presented as posterior mean with 95% creditable interval, probability of any benefit or any harm, and the probability of clinical important benefit. Any benefit is defined as the difference between two arms is greater than zero. Any harm is defined as the difference is smaller than zero. The threshold for clinical important benefit is chosen at 0.75. A significant probability of benefit or harm (clinical important benefit) will be declared above 95%.

Sensitivity analysis

Clinicians were uncertain about whether they would expected differences between the modified intervention and the original intervention. Therefore, we will also investigate the potential impact of the modified intervention compared to the original intervention. To determine this, we will perform a sensitivity analysis by examining the interaction effects between the original intervention and the number of months under the modified intervention. We use the same model as our primary analysis, adjusting for atreatment indicator (under the original intervention) and the interaction between being on treatment and the number of months exposed under the modified intervention. This analysis will allow us to understand the impact of the duration of exposure to the modified intervention. Our goal is to compare individuals who received the 12-month modified intervention and those who received the 12-month original intervention by leveraging the partially exposed data. The sensitivity analysis will involve the following steps:

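### Clinically important benefit must exceed 0.75 with over 95% posterior probability, but 0.75 is also the design effect, so the >80% power does not apply to that claim

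*Protocol*

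**What the plan says.** Protocol 8.3 gives a total of 234 (117 per arm) and claims "more than 80% power of detecting a between-group change in mean score for self-efficacy with diabetes management (SEDM) of 0.75". The basis follows: "this accounts for 20% loss to follow-up at the 5% significance level (alpha) using a two-sample equal-variance t-test". No SD is stated.

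Protocol 8.5.2 analyses 12-month SEDM with a Bayesian linear mixed model adjusted for baseline SEDM. It defines two levels of benefit. For the first, "Any benefit is defined as the difference between two arms is greater than zero". For the second, "The threshold for clinical important benefit is chosen at 0.75". The decision rule is then "A significant probability of benefit or harm (clinical important benefit) will be declared above 95" per cent. The section does not state the prior on the treatment effect.

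Protocol 8.4 explains the choice of a Bayesian analysis: "The conventional frequentist analyses are often interpreted in a dichotomous matter". It adds that absence of evidence gets mistaken for evidence of absence.

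**The concern.** One number does two jobs. In 8.3, 0.75 is the true effect the trial is planned around. In 8.5.2, 0.75 is the value the effect must be shown to exceed, with more than 95% posterior probability. If the intervention works exactly as planned, the posterior for the difference centres on about 0.75 and the probability of lying above 0.75 centres on about 50%. It will seldom pass 95%.

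The two sections together invite the inference that the trial has more than 80% power to show clinically important benefit, and nothing in 8.3 corrects it. At stake is the report of a trial that goes to plan. It would usually state that clinically important benefit was not declared, and some readers may take that as evidence against a worthwhile effect. Section 8.4 says the Bayesian approach was adopted to avoid that kind of misreading.

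**Working it through.** **Inputs from the protocol**
- Design effect 0.75; 117 per arm; 20% loss; 5% alpha; two-sample t-test; power above 80% (8.3).
- Threshold for clinically important benefit 0.75; any-benefit threshold 0; declaration bar 95% (8.5.2).

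**Assumptions, because the protocol gives no figure**
- Two-sided alpha.
- SD of SEDM: 1.5 to 2.0 shown.
- Correlation r between baseline and 12-month SEDM: 0 to 0.7.
- Prior: vague, with zero-centred normal priors as a check.
- Normal approximation; clustering by clinic ignored.

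**1. The plan's own figure.** Evaluable per arm: 117 × 0.8 = 93.6, taken as 93. The power cannot be reproduced directly without an SD. Solving the t-test for exactly 80% at a difference of 0.75 gives SD ≈ 1.82. Smaller SDs give more power (92% at SD 1.5) and larger ones give less (72% at SD 2.0). So the claim of more than 80% is consistent with an SD up to about 1.82.

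**2. The rule for clinically important benefit.** Under a vague prior the posterior is approximately normal around the estimate, with standard error SE. Then P(difference > 0.75 | data) > 0.95 exactly when

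estimate > 0.75 + 1.645 × SE.

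For a true difference δ, the chance of declaring is 1 − Φ(1.645 − (δ − 0.75)/SE). At δ = 0.75 the SE drops out:

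1 − Φ(1.645) = 0.05.

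This was computed as 5.0% for 50, 93, 117, 500 and 5000 per arm and for SDs of 1.5, 1.82 and 2.0. A simulation with estimated variance gave 4.8% to 5.1%.

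**3. Dependence on the prior.** With a normal prior centred on zero with SD τ, 93 per arm, outcome SD 1.82 and a true 0.75:

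| τ | Chance of declaring |
|---|---|
| 2 | 4.4% |
| 1 | 2.9% |
| 0.5 | 0.4% |

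These rates rise towards 5% as the sample grows. A prior favouring benefit would give more than 5%.

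**4. What the bar requires.** SE = SD × √(1 − r²) × √(2/93). The true difference needed for an 80% chance is 0.75 + (1.645 + 0.842) × SE = 0.75 + 2.487 × SE.

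| SD | r | SE | Estimate must exceed | Chance at true 1.0 | True difference for 80% |
|---|---|---|---|---|---|
| 1.82 | 0 | 0.267 | 1.19 | 24% | 1.41 |
| 1.82 | 0.7 | 0.191 | 1.06 | 37% | 1.22 |
| 1.5 | 0 | 0.220 | 1.11 | 31% | 1.30 |
| 1.5 | 0.7 | 0.157 | 1.01 | 48% | 1.14 |

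The range 1.14 to 1.41 is about 1.5 to 1.9 times the design effect.

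**5. The any-benefit rule at a true 0.75.** The chance is 1 − Φ(1.645 − 0.75/SE). Without baseline adjustment it is 96% (SD 1.5), 88% (SD 1.82) and 82% (SD 2.0, which already exceeds what the stated power allows). With r = 0.7 it is 99% or higher at SD 1.5 and 1.82. These values exceed the t-test power because a 95% posterior bar corresponds to a one-sided 5% test.

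**The case against.** The strongest reply is that 5% is what a threshold claim ought to give. The claim is that the difference is greater than 0.75. When the truth is exactly 0.75 that claim is false, and 5% is its boundary error rate. A demanding bar for a stronger claim can be a deliberate choice, and larger true effects do meet it. This stands, and it is why the rule is not a statistical error. It does not remove the need to say how the rule behaves at the effect the trial is planned on.

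A reader might infer that the >80% power figure is wrong or that the trial is underpowered. The documents support neither. Section 8.3 ties the power to a two-sample t-test, which conventionally tests against zero, and the any-benefit claim is well covered. A reader might also infer that the bar can never be met. It can, at larger true effects.

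It is fair, too, that 8.5.2 already commits to reporting the posterior mean, the credible interval and the probability of clinically important benefit, so readers will see more than the verdict. That softens the harm, and how readers would take a non-declaration is a judgement, not something the documents show. Nor does 8.4 rule out every declaration, since the any-benefit verdict is equally dichotomous.

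The prior and operating characteristics may be set out in a statistical analysis plan that is not at hand, so their absence is not the point. The threshold, the bar and the power statement are all fixed in the protocol. Finally, the bracket in the 95% sentence is loosely worded. Applying the bar to clinically important benefit is the natural reading, and any other reading would also call for a clearer sentence.

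**Conclusion.** The point holds, at should-fix level. Under a vague prior, a true difference equal to the design effect leads to a declaration of clinically important benefit about 5% of the time. That result does not depend on SD, baseline correlation or sample size, so more patients would not change it. It does depend on the prior: one centred on zero lowers the rate and one favouring benefit raises it.

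The power in 8.3 belongs to the comparison with zero and does not carry over to the stronger claim. The any-benefit claim keeps about 82% to 99% at a true 0.75 for assumed SDs of 1.5 to 2.0. An 80% chance of the stronger claim needs a true difference of roughly 1.1 to 1.4, for assumed SDs of 1.5 to 1.82 and baseline correlations of 0 to 0.7. The upper end uses the largest SD compatible with the stated power, so it is the unfavourable end of the range. The primary estimate, the sample size and the any-benefit conclusion are unaffected.

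**What to change.** In 8.5.2, keep the declaration above 95% for any benefit and any harm. Report the posterior probability that the difference exceeds 0.75, with the credible interval, and attach no declare/not-declare verdict to it.

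Alternatively, keep the bar and say it is a deliberately strict claim. Then state its operating characteristics under the actual prior and the SD used for planning, including the chance of declaring at a true 0.75 (about 5% with a vague prior) and the true difference that gives an 80% chance. The 1.1 to 1.4 range above rests on assumed SDs and should not be copied into the protocol.

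In either case, reword the bracketed 95% sentence so that it says which claims it covers. In 8.3, add that the power of more than 80% refers to a difference from zero, that is, to any benefit.

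The cost is a few sentences, with no extra participants or data. The protocol loses, or has to qualify, one declared claim. The change should be settled before outcome data are analysed by arm.

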- (1) Calculate the posterior probability of the difference between the estimated effect of receiving 12 months of the modified intervention and 12months of the original intervention being greater than zero. This will determine whether there is any evidence to support the idea that the modified intervention is more effective than the original intervention. If the probability is less than 90%, we can conclude that there is no significant evidence to prove the difference between the two interventions.
- (2) If the posterior probability calculated in step (1) is greater than 90%. We then use our interaction effect model to calculate the posterior probability of any benefit/harm and probability of clinical important benefit of receiving the 12-month original and 12-month modified interventions separately as a supplement to the primary analysis.

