8.5.5 PLANNED INTERIM ANALYSES

An interim analysis within the process evaluation is planned to be performed on user engagement and participant satisfaction with the KiT intervention 3 or 6 months after the start of the intervention; timing is contingent on having enough participants enrolled. The interim analysis will be performed by the process evaluation research team, unblinded to the treatment allocation. The results of the interim analysis will be used as feedback information to the research team to make adjustments to the KiT intervention in real-time. These adjustments could be in the form changing the tone of messaging, changing the wording of messages or switching out topics that had the least user engagement, updating or replacing resources or educational content that had the least user engagement or changing the frequency or sequencing of messaging.

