patient partners) to score the answers from 1-5 based on accuracy, safety and a metric known as the global quality score. The validity and reliability of these metrics were established during several rounds of testing with the raters in addition to literature evidence. The LLM chatbot is not a learning model and will only utilize existing resources gathered for the KiT study. Although, since LLMs are stochastic in nature – i.e., may generate different answers to the same question at different times – we will ask each question 3 times. In addition, we want to test the use of LLMs as evaluators of the quality of answers. In order to do this, we will ask an LLM evaluator to also grade the answer to questions based on the aforementioned criteria, and compare this rating to the human raters. If successful, we plan to have the LLM evaluator continuously assess the questions asked by participants for any sensitive information (e.g., pertaining to suicidal ideation) and the quality of answers given, and flag any potentially harmful case for human review during the study.

It should also be noted we have previously assessed a prototype version of the KiT LLM and an LLM Evaluator (using GPT-4 accessed through UHN's Microsoft Azure subscription) on a set of synthetic questions, with promising results. We are in the process of improving these applications based on feedback from this initial assessment. Examples of these updates include stronger language on recommending visits to the emergency department in certain cases and explicit instructions to consider suicidal ideation when flagging potentially sensitive questions. We plan to test updated versions of the KiT and Evaluator LLMs with the questions already asked by participants during the study.

The English safety testing has been completed and the results are below. Once this amendment is approved them the LLM chatbot will be incorporated in Ontario sites.

English safety testing conclusions (please see accompanying PowerPoint presentation in CTO application)

Common questions to all raters (39 participant questions +12 synthetic questions)

- When considering the full set of questions (39 participant, 12 synthetic), the KiT LLM seems to perform well, with high scores in most metrics, particularly Safety.
- Overall the LLM Evaluator seems to act as, or more, conservative than most human raters (the exception being Patient Partner 2, which was slightly more conservative in general).

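### The modified-versus-original sensitivity model has no time term shared with controls, and its 12-month-original result is an extrapolation if the modification comes by month 12

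*Protocol*

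**What the plan says.** Protocol section 8.5.2 compares 12-month SEDM between arms, pooling original and modified versions, with a Bayesian linear mixed model "controlling for baseline SEDM", adjusted for sex and gender and allowing for clustering by clinic.

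For the question of whether the modified version works better, the section states: "We use the same model as our primary analysis". It then adds a treatment indicator and "the interaction between being on treatment and the number of months exposed under the modified intervention". The aim is to "compare individuals who received the 12-month modified intervention and those who received the 12-month original intervention by leveraging the partially exposed data".

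Step (1) takes the posterior probability that 12 modified months beat 12 original months. Its rule is: "If the probability is less than 90%, we can conclude that there is no significant evidence". Above 90%, step (2) reports probabilities of benefit, harm and clinically important benefit separately for 12 months of each version, as a supplement to the primary analysis.

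On timing, section 8.5.5 places the interim look at engagement "3 or 6 months after the start of the intervention" but makes this depend on having enough participants enrolled. Section 8.1 puts the process evaluation between 3 and 12 months after launch, with a similar condition. The schedule of activities (section 1.2) marks modifications at 3 and 6 months, made in real time and only if needed. Section 5.4 gives 21 months of recruitment and a 12-month intervention period.

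**The concern.** A change made to the live intervention on a calendar date gives each participant a number of modified months fixed by when he or she enrolled. Controls have zero in the interaction column whatever their enrolment date, so they act as one time-constant reference and contribute nothing to the months slope. That slope is a non-randomised early-versus-late comparison within one arm. Controls enrolled over the same calendar period, randomised 1:1 within site, could separate drift from modification, but the listed terms do not use them for this.

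At stake is a rule that can declare the modified version better, and then release version-specific benefit probabilities, when only the case mix or the general level of SEDM has moved. A downward drift would do the reverse and hide a real gain.

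A second problem is support. The contrast and step (2) are defined at 12 months of the original version, an exposure that nobody may have had.

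**Working it through.** **The plan's own figure.** Section 8.3 gives 117 per arm, 20% loss, a difference of 0.75 and more than 80% power, with no SD. Evaluable per arm: 117 × 0.8 = 93.6, taken as 93. The largest SD compatible with 80% power is 0.75 / [(1.96 + 0.8416) × √(2/93)] ≈ 1.83, or 1.82 with the t-test. The protocol states no operating characteristics for the sensitivity analysis.

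**Assumptions.** SD 1.82; baseline–outcome correlation 0.5, so residual SD = 1.82 × √0.75 = 1.576; 93 analysed per arm; uniform accrual over 21 months; one modification at month *c* after launch; no true modification effect; linear drift of *D* points over accrual. Only the sample size and accrual length come from the protocol.

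**Exposure.** For enrolment month *e* and *c* ≤ 12, months under the original version are U = max(*c* − *e*, 0), and M = 12 − U.

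- The longest original exposure is *c* months: 3 if *c* = 3, 6 if *c* = 6.
- The share with a full 12 original months is max(*c* − 12, 0)/21: 0% for *c* up to 12, 3/21 = 14% at month 15, 6/21 = 29% at month 18.

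**Bias of the 12-month contrast in the model as written**, for drift arising after baseline: 12 × (D/21) × Cov(e, M)/Var(M), with E[U] = c²/42, E[U²] = c³/63 and Cov(e, M) = 10.5 × E[U] − c³/126.

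- *c* = 6: Var = 3.429 − 0.735 = 2.694; Cov = 9.000 − 1.714 = 7.286; bias = 1.545 × D.
- *c* = 12: Var = 27.429 − 11.755 = 15.673; Cov = 36.000 − 13.714 = 22.286; bias = 0.8125 × D.

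**Standard error as written:** 12 × 1.576 / √(93 × Var) = 1.20 at *c* = 6 and 0.50 at *c* = 12 (simulation: 1.22 and 0.50).

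**Chance of crossing 90%:** 1 − Φ(1.2816 − bias/SE).

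| Modification month | Drift D | Bias | False declaration |
|---|---|---|---|
| 6 | 0 | 0 | 10% |
| 6 | 0.25 | 0.39 | 17% |
| 6 | 0.5 | 0.77 | 26% |
| 12 | 0 | 0 | 10% |
| 12 | 0.25 | 0.20 | 19% |
| 12 | 0.5 | 0.41 | 32% |

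Simulation of the same model gives about 18–31% over these drifts, which agrees with the closed form within simulation error. With D = −0.5 the rate falls to about 2–3%.

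**Drift shared with baseline.** Adjustment removes a fraction equal to the correlation, here about half. For D = 0.5 the bias becomes about 0.39 (*c* = 6) or 0.20 (*c* = 12), the same as the 0.25 rows.

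**With M as a main effect in both arms.** The interaction becomes a difference between two arm-specific slopes. Common drift cancels, and simulated declaration rates return to about 9–11%. The standard error rises by about √2: 1.22 to 1.73 at *c* = 6, 0.50 to 0.71 at *c* = 12.

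**The case against.** Several points on the other side are sound.

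- **The drift is assumed.** Nothing in the protocol points to a secular change in SEDM, and 0.5 points is two thirds of the 0.75 threshold. Without drift the rule runs at about 10%. Baseline SEDM, sex, gender and clinic absorb part of any change in recruitment mix. This stands, and limits the point to unabsorbed drift.
- **Precision.** The added term costs more variance than it removes in squared bias, even at 0.5 drift: at month 12 the root mean squared error is √(0.50² + 0.41²) = 0.65 as written against 0.71; at month 6 it is √(1.22² + 0.77²) = 1.44 against 1.73. That would matter if the aim were a point estimate. Here the output is a declaration that one version is better, so the false-declaration rate counts for more.
- **Partial exposure was foreseen.** The authors say so. But that wording does not tell the reader that the 12-month-original end of the contrast may lie outside the data.
- **An SAP could add a time covariate.** It could, but the protocol itself states the added terms, the contrast and the decision rule.

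Three stronger readings are tempting but unsupported. One is that nobody can have 12 months of the original version. Section 8.5.5 dates the interim look, not the modification, and makes even that depend on enrolment; a modification at month 15 would leave 14% with full original exposure. Another is that the chatbot makes the modification date differ by province. Section 9 does say that "the LLM chatbot will be incorporated in Ontario sites" ahead of Quebec, but no section counts the chatbot as a modification, and section 8.5.5 does not list it among the possible adjustments. Months exposed are in any case a per-participant count that can use site dates. The third is that the primary result is affected. It pools both versions against randomised controls, so it is not.

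**Conclusion.** The point holds for the sensitivity analysis only. As specified, the model cannot separate a modification effect from calendar drift, although the randomised controls needed to do so are in the data. The size depends on an undocumented drift: a post-baseline change of 0.25 to 0.5 points over accrual takes the 90% rule from about 10% to about 18–31% false declarations, and a drift shared with baseline produces about half the bias. SD, correlation, uniform accrual and drift are all assumptions.

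Separately, and whether or not there is drift, a modification at or before month 12 leaves no participant with 12 months of the original version. Step (2) would then report that version by linear extrapolation. For a modification at month 6, the standard error of the 12-versus-12-month contrast is about 1.2, larger than the 0.75 threshold for clinically important benefit.

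**What to change.** In the sensitivity model of section 8.5.2, add calendar months of follow-up after the modification date as a main effect in both arms; controls receive the value that their own enrolment date implies. The interaction then estimates how the concurrent randomised contrast changes with modified exposure. Enrolment date in both arms is an alternative, but it relies more on drift being linear. Report version-specific effects, including step (2), only over the range of months actually observed. Drop the 12-month-original result unless some participants had that exposure.

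The cost is one model term and no new data. The standard error of this contrast rises about 40% (0.50 to 0.71 for a modification at month 12, 1.22 to 1.73 at month 6), so a true difference between versions will be harder to show. The primary analysis does not change.

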1.2 SCHEDULE OF ACTIVITIES (SOA)

Table 1: Schedule of activities for KiT intervention

Time Point	Enrolment/ Randomization (21 month randomization period)	Intervention Period (12 months)				End of intervention
	-1 week	0	3 months	6 months	12 months	
ENROLMENT						
Eligibility screen	X					
Informed consent	X					
Randomization	X					
INTERVENTION*						
Active arm		X	X	X	X	
Control arm						
ASSESSMENTS						
KiT						
Demographics survey		X		X	X	
READY		X		X	X	
SEDM		X		X	X	
Barriers to Diabetes Adherence (BDA) in Adolescence Stigma subscale		X		X	X	
T1D-related hospitalization (OHIP/RAMQ)					X	
T1D-related ED visits (OHIP/RAMQ)					X	
Process Evaluation			X	X	X	
KiT modifications**			X	X		
Cost of implementation analysis			X	X	X	

*only participants in the active arm will receive the KiT intervention during the 12-month intervention period. Both study arms will receive usual medical care during 12-month intervention period.

**will occur in real-time and only if results of process evaluation reveal modifications or adjustments are required to improve user engagement and satisfaction

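### Sensitivity analysis of modified versus original KiT: step (1) looks only for the modified version being better, yet concludes no evidence of any difference, even when it is clearly worse

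*Protocol*

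**What the plan says.** The primary analysis in section 8.5.2 compares all intervention participants with control, "regardless of original or modified". It defines both benefit and harm and declares either when its probability is above 95%.

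The sensitivity analysis that follows is motivated without a direction: "Clinicians were uncertain about whether they would expected differences between the modified intervention and the original intervention". Its aim is equally open: "we will also investigate the potential impact of the modified intervention compared to the original intervention". The model adds an interaction between treatment and months spent on the modified version. It then contrasts 12 months of modified with 12 months of original.

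- **Step (1)** calculates the posterior probability that modified minus original is above zero. It explains: "This will determine whether there is any evidence to support the idea that the modified intervention is more effective than the original intervention". It then gives the rule for a low value: "If the probability is less than 90%, we can conclude that there is no significant evidence to prove the difference between the two interventions".
- **Step (2)** is conditional: "If the posterior probability calculated in step (1) is greater than 90" per cent. Only then will the team "calculate the posterior probability of any benefit/harm and probability of clinical important benefit" for each version separately.

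The footnote to the schedule of activities (section 1.2) says modifications are made "only if results of process evaluation reveal modifications or adjustments are required to improve user engagement and satisfaction". Section 8.5.5 places the interim review at 3 or 6 months after the start, depending on enrolment, and lists changes to tone, wording, topics, resources, frequency and sequencing.

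**The concern.** A posterior probability near 0 is as strong evidence of a difference as one near 1. The rule treats the two ends differently: above 90% leads to version-specific results, while everything below, including 1%, is labelled as no significant evidence of a difference. The gate is also narrower than what it controls, since step (2) is meant to report harm as well as benefit but opens only on evidence of improvement.

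Worsening is not excluded by design. Modifications are selected on engagement and satisfaction, not on the SEDM score, and a more engaging message set need not raise self-efficacy.

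If a modification does lower SEDM, the pooled estimate is diluted. Beside it would stand a prespecified statement that there is no significant evidence the versions differ. The figures that could show the original version working would not be calculated.

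**Working it through.** **1. The rule on its own terms.** There is no stated figure to reproduce, because the point is a decision rule. For a normal posterior with estimated difference d (modified minus original) and standard error SE, P(better) = Φ(d/SE). Step (2) opens if this exceeds 0.90, that is, if d/SE > 1.2816.

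| d/SE | P(better) | P(worse) | Rule as written | 90%/10% rule |
|---|---|---|---|---|
| −3 | 0.00135 | 0.99865 | no significant evidence | step (2) |
| −2.33 | 0.00990 | 0.99010 | no significant evidence | step (2) |
| −1.645 | 0.04998 | 0.95002 | no significant evidence | step (2) |
| 0 | 0.50 | 0.50 | no significant evidence | no significant evidence |
| +3 | 0.99865 | 0.00135 | step (2) | step (2) |

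Equal evidence in opposite directions gets opposite treatment. If the true difference is −3 SE, step (2) is reached with probability 0.000009 as written and 0.957 under a 90%/10% rule. At −2 SE the figures are 0.0005 and 0.764. This part needs no assumption about the trial's data.

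**2. How often it could matter.**

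Inputs from the protocol:
- 117 per arm with 20% loss: 117 × 0.8 = 93.6, taken as 94 (section 8.3).
- Recruitment over 21 months and 12 months per participant.
- Difference of interest 0.75 (sections 8.3 and 8.5.2).
- Launch of the modification at month 3 or 6 (section 8.5.5).

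Assumptions:
- SD 1.8. Section 8.3 states none. With two-sided 5% and 80% power, the largest SD that fits is 0.75 / ((1.960 + 0.842) × √(2/94)) ≈ 1.83.
- Baseline correlation 0.5, uniform enrolment, a single modification, and no site, sex or gender terms.
- Launch months 12 and 18, for the case where slow enrolment delays the change.

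Formulas:
- Residual SD = 1.8 × √(1 − 0.5²) = 1.559.
- Months on modified = enrolment month + 12 − launch month, limited to 0–12; exposure fraction = this / 12.
- SE of the 12-month difference = 1.559 / (√94 × SD of the exposure fraction).
- If modified is truly 0.75 worse, probability that P(worse) exceeds 90% = Φ(0.75/SE − 1.2816).

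| Launch month | 3 | 6 | 12 | 18 |
|---|---|---|---|---|
| SD of exposure fraction | 0.052 | 0.137 | 0.330 | 0.387 |
| SE | 3.12 | 1.18 | 0.49 | 0.42 |
| Formula (unrounded SE) | 14.9% | 26.0% | 60.2% | 70.0% |
| Simulation, flat prior, 10,000 trials | 14.8% | 26.5% | 59.3% | 69.3% |
| Simulation, N(0,1) prior on the difference, 4,000 trials | 0.0% | 8.4% | 53.4% | 65.6% |
| Range over SD 1.2–1.82, correlation 0.3–0.7, flat prior | 14–20% | 24–45% | 54–94% | 63–98% |

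Every trial counted here ends in the no-evidence conclusion. Rates are low at months 3 and 6 because no participant then has more than 3 or 6 months of the original version, so its 12-month effect is extrapolated.

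**3. The harmful combination.** Take an original effect of 0.75 and a modified effect of 0 (flat prior). The pooled analysis declares any benefit in 5.4%, 7.5%, 24.4% and 58.4% of trials. The combination of interest is: pooled benefit not declared, P(worse) above 90%, and a skipped step (2) that would have shown over 95% probability of benefit for the original. It occurs in 7.4%, 14.6%, 34.3% and 23.7%.

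**The case against.** The best defence is that step (1) asks a one-directional question. It calculates the probability of a positive difference and says this addresses whether the modified version is more effective, so the difference in the next sentence may mean that positive difference. A superiority gate is a legitimate choice for changes meant to improve the product. The probability itself will be calculated, and a reported 1% shows its own direction. The interaction coefficient is estimated before any gate.

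The size can also be challenged. A worsening of 0.75 equals the whole threshold for clinically important benefit, which is a lot for changes of tone, wording or topic. With a worsening of 0.25, P(worse) exceeds 90% in only 12%, 15%, 22% and 25% of trials, against about 10% with no difference. The 7% figure for the harmful combination at month 3 is close to noise: with neither version having any effect, it still occurs in 4.7%. With effects of 0.75 (original) and 0.50 (modified), it occurs in only 2%, 3%, 4% and 2%.

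The points on size stand: at the launch months the protocol names, the practical effect is modest. The one-directional reading does not rescue the text. The conclusion is worded about the difference between the interventions, not about lack of superiority. The stated motive has no direction, and the gate still suppresses harm results that step (2) is meant to supply. Even on that reading, the conclusion sentence needs correcting.

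**Conclusion.** The rule is wrong as written and should be fixed. That follows from the text alone: no lower bound appears anywhere in the protocol, so a 99% probability that the modified version is worse leads to a statement of no significant evidence of a difference. This is not detail left to a statistical analysis plan, because the protocol itself fixes the threshold, the conclusion and the gate.

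The scope is limited to a supplementary analysis. For a true worsening of 0.75, the misreported share is about 15–26% of trials at the named launch months and 59–69% if the change comes at month 12 or 18. These rates rest on the assumed SD, correlation, flat prior, uniform enrolment and single modification. They fall with a sceptical prior or a smaller worsening.

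**What to change.** In section 8.5.2, replace the last sentence of step (1) and the condition of step (2) with: *If this probability is above 90% (modified better) or below 10% (modified worse), go to step (2). If it lies from 10% to 90%, conclude that there is no significant evidence of a difference in either direction.*

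If a one-directional question is really intended, the minimum correction is to limit the conclusion to no significant evidence that the modified intervention is more effective. Running step (2) whatever the result would then remove the gating problem.

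The cost is two sentences, with no extra participants or data and no effect on the primary analysis. With no true difference, entry to step (2) rises from about 10% to about 20% under a flat prior. With an N(0,1) prior on the difference, it rises from about 3% to 6% at launch month 6 and from about 8% to 15% at month 12. If that is unwelcome, a 95%/5% rule keeps chance entry at 10% under a flat prior. It still reaches step (2) with probability 0.912 at a true difference of 3 SE (0.957 under 90%/10%) and 0.639 at 2 SE (0.764). The change should be made before outcome data are analysed by arm.
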